ii. Visit 2: 6-month BP Measurement Assessment and Medication Use

A follow-up visit will be conducted by study staff in all three arms approximately 6 months after enrollment (allowing for a one-month window). BP measurements will be conducted by study nurses independently from the CHW program using standardized Omron BP cuffs. Three measurements will be taken from the seated position with five minutes between each measure [14]. At the 6-month visit we will additionally collect data on medication regimen changes and adherence (Table 1).

iii. Visit 3: 12-month BP Measurement Assessment and Evaluation of BP Device Function

A final home-based study visit in all three arms will be conducted 12 months after enrollment (allowing for a one-month window period). BP measurements will be conducted using standardized Omron BP cuffs by study staff, independently of CHW

interactions with study participants. Three measurements will be taken from the seated position with five minutes between each measure [14]. We will also collect data on self-reported medication regimen changes, adherence, quality of life, and resource use (Table 1).

iv. Extension phase and additional study visits: 18 and 24-month BP Measurement Assessment and Evaluation of BP Device Function

At the conclusion of the 12-month study visit, individuals in the community-based blood pressure arms will be invited to consent for a continuation phase of the project to assess the longer-term impacts of the project. The extension phase will coincide with the period when initial participants complete their 12-month visit to the conclusion of all participants completing 12 month visits. Participants who agree to this continuation will remain in the community-based program, retain their BP cuffs, and be visited by CBPMs with their blood pressure treatment monitored by clinic nurses. For those who consent to the extension phase, study team members will continue home-based visits every 6 months to monitor blood pressure readings and complete questionnaires for study purposes.

v. Missing and Late Appointments

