(3a) Building on the qualitative research conducted before and early in the trial, we will conduct additional qualitative research to assess the acceptability of the interventions and quantitative monitoring of implementation throughout the trial to assess fidelity and sustainability.

(3b) We will record the costs of care and of the interventions and determine the cost-effectiveness of the intervention with microsimulation model (CVD PREDICT) that uses individual-level risk factor data and health cost inputs.

A. Methods

a. (Aim 3a) Fidelity, Sustainability, and Acceptability

The use of the CMIR and TFA (Aim 1) will be extended to evaluate the overall acceptability, fidelity, and sustainability of the intervention.

Approximately 12 months after the start of the trial we will conduct key informants interviews and individual interviews with health workers and trial participants. Where appropriate we will include the same individuals sampled for Aim 1, to compare their experiences during the trial with their initial expectations and preferences. Qualitative data collection and analysis will be similar to Aim 1 methods, adapted as necessary to accommodate unforeseen issues that arise during the trial.

Study documentation (e.g. coordination meeting minutes, supervision visit reports) will be reviewed to extract any relevant information contributing to document adaptations to implementation, and thereby fidelity, decision-making process and thereby acceptability (and feasibility), and short-term sustainability.

These qualitative data will be complemented by collection of quantitative indicators of fidelity and sustainability of implementation. An assessment of the intervention's fidelity will be performed 6 and 12 months after study enrollment (based on monthly data collection), while sustainability will be measured at the 12-month, 18-month, and 24-month visits. Data will be collected through repeated completion of intervention fidelity clinic checklists to estimate adherence, exposure, and quality of the intervention.

b. (Aim 3b) Cost-effectiveness

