Persons who participated in Aim 1 activities and who will participate in Aim 3 activities, will be re-consented regardless of whether they provided verbal or written consent in Aim 1. Consenting procedures for Aim 3 will be identical to those described in Aim 1.

- b. (Aim 3b) Cost-effectiveness
This will be included in the consent to participate in the trial.

H. Data Collection

- a. (Aim 3a) Fidelity, Sustainability, and Acceptability
Data on fidelity outcomes will be obtained from study checklists and data collected with the electronic hypertension management tool in the intervention arms at 6, 12, 18 and 24 months. Sustainability measures, including changes in systolic blood pressure, will be collected using the same sources at 12 months in the intervention arms. In the standard of care arm changes in systolic blood pressure at 12 months and medication use will be obtained through participant chart reviews. All data will be combined into a database for analyses and all personal identifiers will be removed prior to analysis. Interviewers will use guides with open-ended questions to collect qualitative data on the overall acceptability of the intervention.
- b. (Aim 3b) Cost-effectiveness
Resource allocation assessments in all three study arms will be conducted at 6 and 12 months after the start of the trial using a time and motion study over five clinic days, along with medical records reviews and participant exit interviews. Using these measurements, the public-sector unit costs for managing hypertension will be calculated, including human resources, diagnostics and supplies, therapeutics, and home blood pressure monitors. Costs will be collected from relevant sources, including clinic sites, the South African

Department of Health, and published reports. A societal perspective will be applied to data collection and analysis.

I. Analysis

a. (Aim 3a) Fidelity, Sustainability, and Acceptability

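### Aim 3a gives two opposite schedules for fidelity and sustainability, and the 18- and 24-month visits, which have no SOC follow-up, cannot estimate an effect versus SOC beyond 12 months

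*Protocol*

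**What the plan says.** Protocol VI.A.a (Aim 3a Methods) states: "An assessment of the intervention's fidelity will be performed 6 and 12 months after study enrollment". It then says that "sustainability will be measured at the 12-month, 18-month, and 24-month visits".

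Protocol VI.H.a (Aim 3a Data Collection) takes fidelity data from checklists and the "electronic hypertension management tool in the intervention arms at 6, 12, 18 and 24 months". It goes on: "Sustainability measures, including changes in systolic blood pressure, will be collected using the same sources at 12 months in the intervention arms". For SOC, the same paragraph takes the 12-month SBP change and medication use from chart review.

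Table 4 lists the sustainability measures. Those that carry a date are clinics still using cuffs at 12 months, retention in care at 12 months, and SBP change from month 6 to month 12.

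Protocol V.G.b.iv describes the visits after month 12: "individuals in the community-based blood pressure arms will be invited to consent for a continuation phase of the project". Those who consent are visited every 6 months. On duration: "The extension phase will coincide with the period when initial participants complete their 12-month visit to the conclusion of all participants completing 12 month visits". Protocol V.G.b.iii makes month 12 the last scheduled visit in all three arms, with BP taken by study staff on standardised cuffs. The change log (entry of May 29, 2024) describes a prolonged extension for the intervention arms, up to study completion in June 2025.

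SAP section 2 leaves sustainability to a separate analysis plan that is not among the documents. SAP section 10 models SBP and BP control at 6 and 12 months only.

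**The concern.** A team that follows VI.A.a will report sustainability at 18 and 24 months. A team that follows VI.H.a or Table 4 will stop at 12. The choice matters because VI.H.a counts SBP change among the sustainability measures and V.G.b.iv gives the extension the purpose of assessing longer-term impact. Read together, these invite the later BP readings to be taken as evidence that the treatment effect lasted.

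Those readings could not carry that weight. Everyone enters with elevated BP, and the sample-size section itself plans on 30% or 40% control in SOC at 6 months, so improvement without the interventions is expected. A within-arm level cannot separate the two, and a second consent adds selection. The natural fallback is the 12-month comparison, but that is weakened if each arm's SBP comes from a different source.

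**Working it through.** **1. The plan's own figure.** The only design figure is for the 6-month comparison with SOC (Protocol V.J.a): difference 5 mmHg, SD 19, correlation 0.5, alpha 2.5% two-sided, power 80%, loss 20%. With baseline adjustment,

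n = 2 × (2.241 + 0.842)² × 19² × (1 − 0.5²) / 5² = 206 evaluable per arm.

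206 / 0.80 = 257.5, so 258 per arm and 774 in total. This matches the plan. No figure is given for 18 or 24 months.

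**2. The schedules side by side.**

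| Place | Fidelity | Sustainability |
|---|---|---|
| Protocol VI.A.a | 6, 12 months | 12, 18, 24 months |
| Protocol VI.H.a | 6, 12, 18, 24 months | 12 months |
| Protocol Table 4 (dated measures) | none dated | 12 months, or 6 to 12 months |

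All three are current text. Table 4 agrees with VI.H.a on sustainability and not with VI.A.a.

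**3. Who can be seen after month 12.** Under V.G.b.iv the extension is for the two community-based arms: 2 × 258 = 516 randomised participants, less losses and refusals. Planned SOC participants at 18 or 24 months: 0 of 258. With no SOC data, the difference from SOC cannot be estimated at those visits, whatever the size of the intervention groups.

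**4. Reach, as an illustration only.** The documents give neither accrual time nor the extension consent rate. Assume even accrual over A months, closure at the last 12-month visit (V.G.b.iv), 80% retained (the plan's 6-month loss figure, borrowed here) and a consent proportion c from 0.5 to 1. A participant enrolled at month u reaches visit m if u + m ≤ A + 12, so the fraction by enrolment date is f = max(0, 1 − (m − 12)/A). The number is 516 × 0.80 × c × f.

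| A (months) | f at month 18 | Seen at 18 | f at month 24 | Seen at 24 |
|---|---|---|---|---|
| 6 | 0 | 0 | 0 | 0 |
| 12 | 1/2 | 103–206 | 0 | 0 |
| 18 | 2/3 | 138–275 | 1/3 | 69–138 |
| 24 | 3/4 | 155–310 | 1/2 | 103–206 |

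For example, A = 12 and c = 1 gives 516 × 0.80 × 0.5 = 206 at month 18. A later closing date, such as the June 2025 completion in the change log, could raise these counts. It would leave the SOC count at 0.

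**5. The source of 12-month SBP.** V.G.b.iii, and SAP section 5, have study personnel measure BP in all participants at 12 months. VI.H.a instead takes SBP change for the intervention arms from the checklists and the management tool, and for SOC from charts. Followed for Aim 3a, VI.H.a makes the source of the outcome depend on the arm.

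**The case against.** The strongest reply is that no misuse is planned. No section sets 18- or 24-month BP against SOC or against baseline. VI.A.a introduces its schedule as indicators of implementation, and measures such as cuff use or home counselling exist only in the intervention arms, so the absence of SOC is no flaw for them. Table 4's SBP measure ends at 12 months, SAP section 10 already compares each intervention with SOC over 12 months, and the details for Aim 3 may sit in the separate plan. All of this stands. It limits the point to what the later visits can support; it does not resolve the conflicting schedules or the conflicting 12-month source.

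A reader might infer more, in four ways that the documents do not support:

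- **A before-after claim.** One could set near-zero control at entry against the planned 45% or 56% in the intervention arms and say the programme will be credited with all of it, instead of the 15 or 16 points between arms. Those are 6-month power assumptions, control is not a Table 4 sustainability measure, and no section plans that calculation.
- **No conclusion about a lasting effect at all.** The randomised 12-month comparison remains available.
- **Late enrollees can never reach these visits.** That follows only under the V.G.b.iv window and an accrual time that the documents do not state.
- **Single-arm data.** Both CBPM and eCBPM+ continue, so a contrast between them, among continuers, is still possible.

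**Conclusion.** The point holds in this limited form. The contradiction between VI.A.a and VI.H.a is certain from the text, as is the conflict between VI.H.a and V.G.b.iii over 12-month SBP in SOC. It is equally certain that the visits after month 12, as planned, have no SOC follow-up and need new consent. They can describe continued delivery and within-arm SBP among continuers, and no more than that with respect to SOC. How many participants would be seen is not known: the ranges above rest on assumed accrual, loss and consent and predict nothing about this trial. The primary outcome at 6 months is unaffected. What is at stake is the meaning of one Aim 3 objective, so the sponsor should correct it, but the trial's main conclusion does not depend on it.

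**What to change.** 1. Reconcile VI.A.a, Table 4 and VI.H.a so that fidelity and sustainability each have one set of time points.
2. Rest any conclusion about a sustained BP effect versus SOC on the randomised three-arm comparison at 12 months, using the study-staff measurements of V.G.b.iii in every arm. Amend VI.H.a so that chart review does not supply the SOC value, nor the management tool the intervention value, for this comparison. If the SAP section 10 model is used, take the 12-month contrast from the model that keeps the arm-by-visit interaction.
3. State, in the protocol or the separate Aim 3 plan, that 18- and 24-month BP results have no SOC comparison, cover only continuers in CBPM and eCBPM+, and are descriptive.
4. Report, by arm, the numbers eligible for each visit by enrolment date, consenting and seen, and the 12-month SBP of those who did and did not continue.

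The cost is some wording and one descriptive table from data the trial will already hold. The downside is a narrower claim about long-term effect. The visits themselves need not be dropped.

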We will evaluate the implementation of two community-based, technology-supported programs to improve blood pressure control in South Africa, guided by the Conceptual Model for Implementation Research [11], with a focus on acceptability (Aim 1), effectiveness (Aim 2) and feasibility, cost- effectiveness and sustainability (Aim 3). We will leverage a 20-year partnership with the Department of Health, a multidisciplinary team of experts, and a recent health screening of approximately 18,000 individuals in the catchment area [5] to accomplish the above goals, and to accomplish the following aims:

Aim 1

Evaluate the acceptability and conduct a readiness assessment for implementation, of community-based hypertension, technology-supported interventions to reduce blood pressure in rural.

Guided by the Conceptual Model of Implementation Research (CMIR), we will use mixed methods to assess organizational, healthcare worker, and participant readiness for implementation of the interventions. We will use results of the readiness assessments to refine final implementation strategies for the intervention.

Aim 2

Determine the effectiveness of a community-based, technology-supported intervention to reduce systolic blood pressure and increase blood pressure control among individuals with uncontrolled hypertension in rural South Africa.

We will conduct a trial using CBPMs in conjunction with in-home BP monitoring among approximately 774 adults randomized to one of three different arms of hypertension care: 1) clinic-based standard of care model (SOC); 2) community blood pressure monitor-based blood pressure monitoring model (CBPM); 3) and enhanced community blood pressure monitor-based model, including mobile health blood pressure monitoring (eCBPM+).

Aim 3

Determine the fidelity, sustainability, acceptability, and cost-effectiveness of community-based, technology-supported hypertension interventions to reduce blood pressure in rural KwaZulu-Natal.

The use of the CMIR (Aim 1) will be extended to evaluate the fidelity and sustainability of the intervention. A microsimulation model (CVD PREDICT) that uses individual-level risk factor data and health cost inputs will be used to determine the cost-effectiveness of the intervention.

IV. AIM 1: READINESS AND ACCEPTABILITY ASSESSMENT

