Sustainability	
 - Number of participants counseled in lifestyle modification and medication adherence at home by CBPMs. - Number of clinics adopting use and distribution of BP cuffs for HBPM. - Proportion of clinics sustaining use and distribution of BP cuffs for HBPM at 12 months, among those who distributed BP cuffs at the start of the study. - Proportion of participants retained in hypertension care at 12 months, among enrolled study participants. - Absolute change in systolic blood pressure (SBP) between 6 and 12 months after enrollment, among enrolled study participants. - Proportion of participants retained in hypertension care at 12 months, among enrolled study participants. - Absolute change in systolic blood pressure (SBP) between 6 and 12 months after enrollment, among all study participants. 	
 - CBPM study records. - Study check lists. - Study check lists. - Participant study records. - CDS records - Participant study records. - CDS records.

C. Data Sources

a. (Aim 3a) Fidelity, Sustainability, and Acceptability

Both the fidelity and the sustainability of the intervention will be assessed using data obtained through review of study check lists, the participant study records (including prescriptions), CDS records, CBPM study records, outreach team leader supervision records, and coordination meeting minutes.

Key informant and individual interviews will assess overall acceptability and experience of the intervention.

b. (Aim 3b) Cost-effectiveness

Cost data will be obtained from trial participant interviews, KZN DoH unit prices, and analysis of intervention delivery.

The trial will provide individual level outcome data on SBP and blood pressure control 6 and 12 months. The PREDICT model will use these data to predict long term effects of the interventions on quality adjusted life years (QALYs)

D. Recruitment

a. (Aim 3a) Fidelity, Sustainability, and Acceptability

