Quantitative data will be analyzed using Stata Statistical Software (Release 17. College Station, TX) and statistics for fidelity and sustainability outcomes will be generated. Qualitative data analysis will be performed using similar methods as in Aim 1. The key informants and individual interviews will be collected in isiZulu, then transcribed, and translated in English by a team of social science research assistants. A data-led coding framework will be developed, based on themes, which emerge from the data. The research assistants involved in collecting the data will work with other social science team members to agree on the coding framework and performing coding of the data. Thematic summaries will be prepared using the data and a process of building consensus among the whole study team. These summaries will form the building blocks for reporting the findings. Organization of data on the acceptability of the intervention will again be organized into component constructs using the Theoretical Framework for Acceptability, as described in Aim 1.

b. (3b) Cost and Cost-effectiveness

Cost-effectiveness of the intervention compared to standard of care in blood pressure management, will be calculated as incremental costs for absolute differences in blood pressure (costs/mmHg) and incremental costs per extra participant with controlled blood pressure. This analysis will be performed using the Harvard CVD PREDICT model [15] for cost-effectiveness and changes in CVD-related health outcomes. The model will be used to assess the cost-effectiveness of the intervention and to model the impact on the observed change in systolic blood pressure on future CVD events. We will also use the model to translate the intervention effectiveness established during the trial into quality adjusted life years (QALY) and applying assumptions about effects of SBP reductions on survival, quality of life, and complications, based on the extant literature and confirmed locally as part of this trial.

The cost-effectiveness will be calculated across the entire intervention, as well as separately by each of the study arms and expressed in incremental cost-effectiveness ratios (ICERs) and quality adjusted life years (QALYs).

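### The Aim 3a sustainability outcome for SBP is a 6-to-12-month change with no contrast against SOC, so it cannot show whether a benefit over usual care was kept

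*Protocol*

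**What the plan says.** Aim 3 is worded as "Determine the fidelity, sustainability, acceptability, and cost-effectiveness of community-based, technology-supported hypertension interventions to reduce blood pressure in rural KwaZulu-Natal". The Sustainability block of Protocol Table 4 has two SBP rows: "Absolute change in systolic blood pressure (SBP) between 6 and 12 months after enrollment, among enrolled study participants" and "Absolute change in systolic blood pressure (SBP) between 6 and 12 months after enrollment, among all study participants". The 12-month retention row also takes all enrolled participants as its denominator. None of these rows names an arm, a comparator or a threshold.

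Protocol VI.H.a gives the data sources. For the two interventions: "Sustainability measures, including changes in systolic blood pressure, will be collected using the same sources at 12 months in the intervention arms", where those sources are study checklists and the electronic hypertension tool. For SOC: "In the standard of care arm changes in systolic blood pressure at 12 months and medication use will be obtained through participant chart reviews". It then says "All data will be combined into a database for analyses". On analysis, Protocol VI.I.a says only that "statistics for fidelity and sustainability outcomes will be generated". Protocol VI.A.a sets the timing: "sustainability will be measured at the 12-month, 18-month, and 24-month visits".

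Other sections bear on the point:

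- Protocol V.G.b plans three seated Omron readings by study staff in all three arms at both 6 and 12 months. The extension to 18 and 24 months is offered to the two community arms only.
- SAP section 2 leaves sustainability to a separate analysis plan.
- SAP 9.1 summarises SBP and its change from baseline by arm at 6 and 12 months, but its regression contrast is at 6 months.
- SAP section 10 fits an exploratory mixed model of each intervention against SOC over 12 months with an arm-by-visit interaction. The interaction is removed if it does not reach p<0.10.

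**The concern.** The benefit of an intervention is its difference from SOC. A 6-to-12-month change within participants is a different quantity. It takes in everything that moves blood pressure between the two visits, such as natural course, ordinary changes of treatment and season. It also carries no information on whether there was a benefit at month 6 to sustain.

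The indicator can therefore look stable when the benefit has gone, and look like a loss when the benefit is intact. Month 12 matters most here, because it is the only sustainability visit with a concurrent randomised control: SOC is not followed at 18 and 24 months. The result is meant to inform adoption by the health service, so a misleading reading would have practical weight.

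**Working it through.** **1. What the change can and cannot distinguish.** The documents give no figures for this outcome, so the values below are assumed for illustration. They are mean changes from baseline in mmHg, in the order SOC / CBPM / eCBPM+, with equal arms. The all-arm figure is the simple mean of the three 6-to-12-month changes. Benefit is the intervention-minus-SOC difference.

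| Case | Month 6 | Month 12 | Change, all arms | Change, intervention arms | Change, SOC | Benefit at 6, then 12 |
|---|---|---|---|---|---|---|
| A. Never a benefit | -10/-10/-10 | -10/-10/-10 | 0 | 0 | 0 | 0, then 0 |
| B. SOC catches up | -5/-10/-10 | -10/-10/-10 | -1.67 | 0 | -5 | -5, then 0 |
| C. Arms converge | -5/-10/-10 | -8.33 in each | 0 | +1.67 | -3.33 | -5, then 0 |
| D. Interventions rebound | -5/-10/-10 | -5/-5/-5 | +3.33 | +5 | 0 | -5, then 0 |
| E. Benefit kept | -5/-10/-10 | -5/-10/-10 | 0 | 0 | 0 | -5, then -5 |
| F. Benefit kept, all drift by 3 | -5/-10/-10 | -2/-7/-7 | +3 | +3 | +3 | -5, then -5 |

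- Averaged over arms, A, C and E all give 0. D and F give similar figures (+3.33 and +3), although the benefit is lost in D and intact in F.
- In the intervention arms alone, A, B and E all give 0.
- With all three arms' changes side by side, A and E are still identical. Only the difference from SOC at both visits separates all the cases.

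**2. Does SAP section 10 already do this?** When the interaction is dropped, the model gives one overall effect. With equal numbers at the two visits, a benefit that falls from 5 to 2.5 is reported as about (5 + 2.5)/2 = 3.75, and the decay is not visible.

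How often the term would survive can be approximated. Take SD 19 and 206 per arm (protocol), and let both interventions lose 2.5 mmHg relative to SOC. The arm means of the 6-to-12-month change are then 0, 2.5 and 2.5, and the sum of squared deviations is 1.667² + 2 × 0.833² = 4.17. The non-centrality is 206 × 4.17 / [2 × 19² × (1 - r)], where r is the correlation between the 6- and 12-month readings. The documents do not give r.

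| r (assumed) | Non-centrality | Power of the 2-df test at 0.10 |
|---|---|---|
| 0.2 | 1.49 | 27% |
| 0.5 | 2.38 | 38% |
| 0.7 | 3.96 | 54% |

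So with half the benefit gone, the term would be dropped in roughly 46% to 73% of trials.

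**3. Precision of the replacement.** The protocol's own sample size fixes the convention. With two-sided alpha 0.025 and 80% power, n = 2 × (2.2414 + 0.8416)² × 19² × (1 - 0.5²) / 5² = 205.9, so 206. Then 206/0.8 = 257.5, so 258 per arm, as stated. I assume the same 206 per arm are available at both visits.

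- *Difference from SOC at 12 months, adjusted for baseline.* Power for 5 mmHg is 80% at a baseline-to-12-month correlation of 0.5, and 69% to 93% over an assumed range of 0.2 to 0.7.
- *Change in the difference, 12 minus 6 months.* SE = 19 × √[2(1 - r)] × √(2/206). The detectable change is 3.083 × SE.

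| r (assumed) | SE | 95% CI half-width (1.96 × SE) | Detectable, 80% power | Power for a 5 mmHg loss |
|---|---|---|---|---|
| 0.2 | 2.37 | 4.6 | 7.3 | 45% |
| 0.5 | 1.87 | 3.7 | 5.8 | 67% |
| 0.7 | 1.45 | 2.8 | 4.5 | 89% |

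**The case against.** The strongest reply is that the trial already makes the controlled comparison. SAP 9.1 shows 12-month SBP by arm, and SAP section 10 estimates each intervention against SOC over 12 months. Its arm-by-visit term is the change in difference asked for here. That is correct, and a reader who inferred from Table 4 that the trial discards its randomised 12-month comparison would be wrong. What remains is that nothing links section 10 to the sustainability outcome, and its interaction may be removed.

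Second, a reader might infer that the plan averages the three arms into one number, or that a change of zero will be declared sustained. The documents say neither. Table 4 gives denominators, combining data in one database is data handling, and no threshold is set. The all-arm column above is therefore only an illustration. The point does not depend on it, because the intervention arms' own change has the same weakness.

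Third, the separate sustainability plan may define the contrast. It may, but it is not among the documents, so Table 4 is the only definition available. It would need to change in any case if that plan departs from it.

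Fourth, Protocol VI.A.a speaks of the sustainability of implementation, and most rows in the block count counselling, cuff use and retention. This limits the weight of the point: SBP is one indicator in a secondary aim. It does not rescue the SBP row, which is an effect measure listed under an aim about interventions to reduce blood pressure.

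Finally, the Table 4 source column includes clinical decision support records, which exist only in the intervention arms, and the table's layout did not survive extraction. Protocol VI.H.a nevertheless provides explicitly for SOC SBP.

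**Conclusion.** The concern holds as a defect in the outcome definition. Table 4 specifies an SBP change without a SOC contrast. A result of 0 in the intervention arms is compatible with a benefit kept at 5 mmHg, lost entirely, or never present. A common drift of 3 mmHg would look like a loss when nothing was lost. The logic needs no distributional assumption; the particular values are illustrative.

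SAP section 10 mitigates this without curing it. Under the protocol's SD and evaluable numbers, its interaction test would detect a halving of a 5 mmHg benefit with only about 27% to 54% power, over an assumed 6-to-12-month correlation of 0.2 to 0.7. Otherwise one averaged effect is reported.

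The primary and secondary outcomes at 6 months are unaffected. The change should be made because it is cheap and month 12 is the last visit with a randomised control.

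The sources also conflict. Protocol VI.H.a takes SOC SBP from charts and intervention SBP from checklists and the electronic tool, while Protocol V.G.b.iii plans study-staff readings in all three arms. A contrast built on the VI.H.a sources would confound arm with method of measurement.

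**What to change.** - **Table 4 and the separate Aim 3 plan.** Replace both SBP rows with the adjusted SBP difference of each intervention from SOC at 12 months, shown beside the same difference at 6 months, and the change in that difference (12 minus 6 months) with its CI. Take these from the SAP section 10 model, with the arm-by-visit term always retained for this purpose. Describe a benefit as sustained only where one was shown at month 6.
- **Data source.** Use the study-staff readings planned in all three arms, and reconcile Protocol VI.H.a with Protocol V.G.b.iii.
- **Retention.** Report 12-month retention by arm against SOC, in the form that SAP 9.3 already uses at 6 months.
- **18 and 24 months.** State that SBP changes at these visits have no concurrent control.

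The cost is wording in Table 4, Protocol VI.H.a and the Aim 3 plan; no new data are needed. The downside is precision. The change in difference will have a 95% interval of roughly ±2.8 to ±4.6 mmHg under the assumptions above, so a moderate loss of benefit may be neither shown nor excluded. The report should say so and should not read a non-significant change as proof that the benefit was kept.
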